1.2 TITLE OF THE STUDY

The combined use of serum Neurotensin and IL-8 as screening markers for

colorectal cancer and adenomas. A prospective study.

1.3 KEY WORDS

IL-8; Neurotensin; Colon cancer; Rectal cancer; Colorectal cancer Screening;

Sensitivity and Specificity.

1.4 STUDY TYPE

Case control study

1.5 SAMPLE SIZE

To be analysed: **n** = 500

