3.2 INCLUSION / EXCLUSION CRITERIA

3.2.1 Inclusion criteria:

Individuals over 50 years of age referred for colonoscopy under any indication.

Over 60 years of age,

Change in bowel habit to looser/more frequent stools,

+/- PR bleeding AND

2 positive FIT/FOB tests.

3.2.1 Exclusion criteria:

a) Need for emergency surgery,

b) Presence of Inflammatory bowel disease,

c) Known history of inherited colorectal cancer,

d) History of cancer in another primary site,

e) Presence of liver metastases (Neurotensin is metabolized in the liver),

f) Negative previous colonoscopy for cancer,

g) Haemolysis in serum samples,

h) Informed consent not signed/withdrawal and

i) Persons who will not have the capacity to decide for

themselves, who are unable to represent their own interests or are particularly susceptible to coercion.

Information concerning performance status, use of statins, steroids or any

anti-inflammatory / immunosuppressive medications will also be collected.

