3.5 PROPOSED SAMPLE SIZE / POWER CALCULATIONS

Assuming that the AUC of the new test is commensurate with the pilot study (AUC=0.85), we calculate the number of samples required to obtain a 95%

confidence interval of size 0.1. We assume that the ROC curve follows a binormal distribution, and that the prevalence of adenoma/cancer is between 20-30% in the study participants. We obtain that we require between 400 (30% prevalence) and 553 (20% prevalence) participants. We therefore target an enrollment of 500 patients. We intend to perform an interim analysis after 50% of the patients have been included and evaluated.

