3.6 FEASIBILITY OF RECRUITMENT

The collaborative departments (Surgical Department and Gastroenterology department) of Royal Preston Hospital and the respective departments from Furness General Hospital screen approximately 18-20 cases per week. Assuming a participation rate of 50%, 500 patients can be recruited during a 12 months' period.

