7. FINANCIAL SUMMARY

Item	Total funding period 12 months (£)	Costs
Kits for Neurotensin, IL-8	6 x human neurotensin ELISA	
	(CSB-E09144h): 2BScientific, 6 x	
	ELISA (enough for 488 samples,	
	allowing for optimization, £ 490	
	each=	Total cost:
	£ 2,940), quote # O-VM-18091101,	£ 4,000
	Cusabio	
	IL-8 from Peprotech	
	https://www.peprotech.com/human-	
	il-8-standard-tmb-elisa-	

	Cusabio offers at £ 520	
One-year Masters by F	Fees are £ 4,260 per annum	Total cost:
research student		£ 4,260
Case payment	• The total costs for processing 200	
(centrifugation at 3000 rpm	blood samples and storage at -20	
for 10 mins, and store at -	or -80 is £3,573	
20°C / -80 °C until assayed.		
ELISA measurements.	Additional lab costs amounting to	Total cost:
	£1500	
		£ 9,600
Research Nurses at both T	Top scale band 5 nurse x 0.25 FTE	
FGH and LTHTR sites. =	=18,395 x 0.25 x2	
Biostatistics S	Statistical consultancy rates range from	
£	285 to £120 UK pounds per hour.	Total cost: from
F	For a total of 20 hours from £ 1700 to £	£ 1,700 £ to
2	2400	£ 2,400
		~ 2,700
Charges for shipping,		Total cost: £ 200
delivery		101a1 COSI: £ 200

8. References

2 Screening for colorectal cancer: U.S. Preventive services task force recommendation statement. Ann Intern Med 2008;149:627-637.

3 Knudsen AB, Hur C, Gazelle GS, Schrag D, McFarland EG, Kuntz KM: Rescreening of persons with a negative colonoscopy result: Results from a microsimulation model. Ann Intern Med;157:611-620.

4 Hassan C, Giorgi Rossi P, Camilloni L, Rex DK, Jimenez-Cendales B, Ferroni E, Borgia P, Zullo A, Guasticchi G: Meta-analysis: Adherence to colorectal cancer screening and the detection rate for advanced neoplasia, according to the type of screening test. Aliment Pharmacol Ther;36:929-940.

5 National Comprehensive Cancer Network, Colorectal cancer screening (Version
2.2013), Accessed 16/12/2013,

http://www.nccn.org/professionals/physician_gls/gl_steering_committee.asp:

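### The same 500 is given as the number enrolled and the number analysed, although exclusions follow enrolment and the costed neurotensin kits cover 488 samples; the effect on precision is small

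*Protocol*

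**What the plan says.** - **Number analysed.** Section 1.5: "To be analysed: n = 500".
- **Number enrolled.** Section 3.5, after deriving a need for 400 participants (30% prevalence) to 553 (20% prevalence): "We therefore target an enrollment of 500 patients". No allowance for loss is stated.
- **Basis of the size.** Section 3.5 takes an AUC of 0.85 from the pilot, a binormal ROC curve, and a 95% "confidence interval of size 0.1".
- **Order of events.** Section 3.1 enrols everyone who meets the inclusion criteria, then applies the exclusion criteria, then draws blood.
- **Exclusions that can act after the draw.** Section 3.2.1 lists "Haemolysis in serum samples" and withdrawal of consent. Section 5.1 allows withdrawal at any time.
- **Assay supply.** Section 7 costs six neurotensin kits at £490 each, "enough for 488 samples" after an allowance for optimisation.

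The protocol gives no loss rate and no rule for replacing excluded participants.

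**The concern.** A precision target is met by the participants who are analysed, not by those who are enrolled. If 500 are enrolled and some are then excluded, fewer than 500 contribute to the primary AUCs. The protocol itself provides for such losses: a haemolysed sample can be recognised only once there is a sample. Separately, even with no exclusions, the costed kits leave 12 of 500 without a neurotensin value, and neurotensin is one of the two primary markers.

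Three figures in the same document (analysed, enrolled, assay capacity) therefore do not fit together. What is at stake is whether the stated precision still holds at the number likely to be analysed, and whether the shortfall is recognised in advance or only at the bench.

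**Working it through.** **Inputs.** From section 3.5: AUC 0.85, 95% confidence, interval width 0.1 (half-width 0.05), binormal ROC, prevalence p of 20-30%. From sections 1.5 and 3.5: 500. From section 7: 488. Assumed, because the protocol gives no rate: loss of 5-10% of those enrolled.

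**Step 1: reproduce the protocol's sample size.** The Obuchowski binormal variance is

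V = 0.0099 · exp(−a²/2) · [(5a² + 8) + (a² + 8)/k], with a = 1.414 · z(0.85) = 1.4655 and k = (1 − p)/p.

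The number of cases is n₁ = 1.96² · V / 0.05², and the total is N = n₁/p.

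- p = 0.30: V = 0.0781, n₁ = 120.0, N = 400.0 (protocol: 400).
- p = 0.20: V = 0.0720, n₁ = 110.6, N = 552.9 (protocol: 553).

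Both figures are reproduced, so this formula with 0.1 as the full width is taken as the protocol's method. The Hanley-McNeil variance gives 338 and 484 and does not match.

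**Step 2: how many can be analysed if 500 are enrolled.**

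- Kits alone, no exclusions: 488, a shortfall of 12 (12/500 = 2.4%).
- Assumed 5% loss: 500 × 0.95 = 475.
- Assumed 10% loss: 500 × 0.90 = 450.

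The last two are below 488. If the lost samples are removed before the assay, the kits are then no further limit.

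**Step 3: interval width at each number.** Width = 2 · 1.96 · √(V/(N·p)). The last column is the lowest prevalence at which the width is no more than 0.1.

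| Analysed | Width, p = 20% | Width, p = 30% | Prevalence needed for 0.1 |
|---|---|---|---|
| 500 | 0.105 | 0.089 | about 22.6% |
| 488 | 0.106 | 0.091 | about 23.2% |
| 475 | 0.108 | 0.092 | about 24.0% |
| 450 | 0.111 | 0.094 | about 25.7% |

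The kit shortfall alone adds about 0.001 to the width. A 10% loss adds about 0.006 at 20% prevalence and 0.005 at 30%.

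**Step 4: what full delivery would take.** To have 500 analysed, 500/(1 − d) must be enrolled for a loss rate d: 500/0.95 gives 527 at 5%, and 500/0.90 gives 556 at 10%.

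**The case against.** **500 may already mean evaluable participants.** Section 3.5 places the interim analysis at half of the patients included and evaluated, and section 4.5 puts that at 250 persons. On that reading, the word for enrolment in section 3.5 is loose. This softens the wording point but does not remove it. Section 3.1 uses enrolment for the step before exclusions, no larger enrolment is stated anywhere, and 488 is below 500 on either reading.

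**The kit count is a budget line.** It sits in a funding table, more kits can be bought, and the same table costs processing for 200 blood samples, so it is evidently not an operating limit. This stands. A reader might infer that 500 analysed cannot be reached, but the protocol supports only that the plan as costed does not deliver it.

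**The consequence is small.** This also stands. Missing 0.1 at 20% prevalence is already plain in section 3.5, which calculates 553 for that case and then chooses 500. Kits and exclusions do not cause it. Section 3.5 also states no width for 500, so no stated width is broken.

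**Stronger readings that a reader might infer, and why they fail:**

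- That the assumed loss comes on top of the 488 ceiling. Samples excluded before the assay use no kit capacity, so the two do not add up unless every excluded sample is assayed first, which the protocol does not say.
- That the last participants recruited go unmeasured. No section fixes the order of assay.
- That recruitment falls short. Section 3.6 has the departments "screen approximately 18-20 cases per week"; at 50% participation over 52 weeks this is 18 × 0.5 × 52 = 468 to 20 × 0.5 × 52 = 520, which brackets 500.

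**Conclusion.** The inconsistency is real and minor. The protocol gives one figure for two different quantities, provides for exclusions between them without an allowance, and costs assays for 12 fewer samples than it says it will analyse. As planned and costed, fewer than 500 participants will have a neurotensin value.

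The formula and its results (400 and 553) are reproduced, and 488, 475 and 450 all lie inside that range, so this does not show the sample size calculation to be wrong. The main practical consequence is that the prevalence needed to meet the 0.1 goal rises from about 22.6% to between 23.2% and 25.7%. At 450 that is just above the midpoint of the assumed 20-30%.

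These figures rest on the protocol's AUC of 0.85 and its variance formula. The values at 475 and 450 also rest on a loss rate of 5-10% that is assumed here. The 488 depends only on the kit line in section 7.

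**What to change.** 1. In sections 1.5 and 3.5, state 500 as the number enrolled and give the number expected to be analysed separately, with the loss assumption behind it and the interval width that follows. For example, an assumed loss of 5-10% gives 450-475 analysed and a width of 0.108-0.111 at 20% prevalence and 0.092-0.094 at 30%.
2. Match the neurotensin kits in section 7 to the number to be assayed, or state 488 as the ceiling on neurotensin values. Six kits for 488 samples is about 81 per kit, so one more would cover the missing 12.

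The cost is two sentences and, if chosen, one kit at £490. The stated size and precision become slightly less favourable. The design does not change.

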1.6 TRIAL DURATION

First patient in to last patient out: 12 months

Duration of the whole trial: 15 months

1.8 THE NEED FOR A TRIAL

Colorectal cancer mortality can be lowered by both early diagnosis and cancer prevention.[1, 2] The objective of screening is to detect cancer at an early, curable stage. Individuals at average risk, those older than 50 years of age, with a negative family history and negative history of adenoma, colorectal cancer, or inflammatory bowel disease are among the highest yield group.

Recent literature proposes that after an initial negative colonoscopy (which is the current standard of screening not only in average risk but also in increased risk patients, should start at age 50 or earlier age with frequency depending on risk factors: e.g. personal/family history of polyps/cancer, inflammatory bowel disease, known genetic syndrome and prior colonoscopy findings), follow-up with rescreening after the age of 60 with annual guaiac fecal occult blood testing, annual fecal immunochemical testing, or computed tomographic colonography every five years provides approximately the same benefit in life-years with fewer complications and at a lower cost.[3] There is a lack of consensus concerning the use of CT colonography as a primary screening tool.

The number of CRC cases from colorectal cancer screening is still rather low. Sensitivity of guaiac tests for the detection of CRC/adenomas is 21.8%-46.3%.(4) Colonoscopy is the favoured screening method for individuals at average risk despite lower patient compliance with this modality. A meta-analysis of 14 randomized controlled trials documented that although endoscopic surveillance was superior to stool testing in detecting advanced neoplasms, its benefit was eclipsed by a lower participation rate.[4] Colonoscopy is the favored screening method for individuals at average risk despite lower patient compliance with this modality. Whilst colonoscopy is an outstanding tool for diagnosing potentially curable bowel cancer, too many patients are currently having an unnecessary procedure as the pick-up rate for bowel cancer is only 4%. Nevertheless, NCCN guideline panelists agree that any form of screening is better than none.[5]

An actual connection between the proposed screening markers and the detection of colorectal cancer and adenomas would have a significant impact on: a) target population compliance, b) re-definition of the cancer pathway for candidate patients by changing the indications for colonoscopy and c) the cost-effectiveness, vital for patients' survival and the sustainability of the NHS, by means of earlier cancer/adenoma diagnosis.

2. INTRODUCTION

Cancer research offers a better insight into regulatory mechanisms involved in cell proliferation in colorectal cancer, and might eventually guide us to new possibilities in terms of novel biomarkers that would facilitate early diagnosis.

Neurotensin (NT) mediates its effects by binding to three neurotensin receptors NTSR-1, -2, and -3: the first two are G-protein coupled receptors, whereas the third belongs to the sortilin receptor superfamily. [6-8] NT via NTSR-1 initiates a multiplicity of intracellular signaling pathways in colon cancer cells and in non-transformed NCM460 colonocytes, as well as the epidermal growth factor receptor (EGFR) and downstream mitogenactivated protein kinases (MAPK) via the metalloproteinase-dependent cleavage of pro- TGF alpha.[9] NT-mediated activation of MAPK signaling and the downstream transcription factor activator protein 1 (AP1) also occurs rapidly in human colorectal cell lines.[10] Moreover, transactivation of the IL-8 promoter is triggered by NT-mediated AP1 activation [10, 11] while NT also stimulates Ras pathway and nuclear factor kappa-light-chain-enhancer of activated B cells (NF-kB) -dependent secretion of IL-8.[6, 12] Intense transcription of the NTSR-1 gene via TCF/Lef- and nuclear β-catenindependent pathways can explain NTSR-1 overexpression in colon cancer.[13] Higher NT levels are also obtained from colon cancers compared to normal colon tissues, and in vivo evidence establishes that NT/NTSR-1 signaling is fundamental for tumor growth.[14]

Gui et al [15] found that NTSR1 expression was considerably increased in both adenomas and adenocarcinomas compared with histologically normal epithelium and in adenocarcinomas compared with adenomas.

Given that colorectal cancer is the second leading cause of cancer-related death in Europe and the third in the USA, a new non-invasive screening modality with the potential for high population compliance at a lower cost than the current screening system and with the capacity for early detection of

colorectal cancer and precursor adenomatous polyps is of paramount importance.[16, 17]

This pilot study aims to investigate whether specific pattern of serum neurotensin/NTSR1/IL-8 values can detect patients with adenomas or colorectal cancer and determine the feasibility of these agents being used as a screening tool.

2.1 EVIDENCE

2.1.1 Serum neurotensin/IL-8 values in colorectal cancer

Serum neurotensin/IL-8 values in the diagnosis of colorectal cancer have been reported for first time in literature by our own group.[18, 19] This pilot study aimed to determine the feasibility of serum neurotensin/IL-8 values being used as a screening tool for colorectal cancer. Fifty-six patients and 15 healthy controls were assigned to seven groups according to their disease entity based on theater records and histology report. Blood samples for neurotensin and IL-8 were measured using an enzyme-linked immunosorbent assay.

There were no differences in the clinical and biochemical parameters of patients and controls. Group (p= 0.003) and age (p= 0.059: marginally significant) were independent predictors of neurotensin plasma values. Neurotensin (p= 0.004) and IL-8 (p= 0.029) differed between healthy and colorectal cancer patients. Neurotensin values differentiated the control group from all remaining groups.

The value of plasma neurotensin ≤54.47 pg/ml at enrollment selected by ROC curves demonstrated a sensitivity of 77%, specificity of 90%, and an estimate of area under ROC curve (accuracy) of 85% in predicting colorectal cancer.

At enrollment, the value of plasma IL-8 ≥8.83 pg/ml had a sensitivity of 85%, specificity 80%, and an estimate of area under ROC curve (accuracy) of 81% in predicting colorectal cancer.

Our results depicted that IL-8 should be used complementary to neurotensin due to its lower specificity. None of the colorectal cancer patients displayed a combination of high neurotensin and low IL-8 values (beyond cutoffs). Unpredictably, 3 out of 13 patients in the colorectal cancer group had neurotensin values above the cut-off value defined by the ROC curve. Notwithstanding, the IL-8 values of the same patients were high and well above the cut-off value, as our analysis anticipated for this group. Two other colorectal cancer group patients unexpectedly had low IL-8 values, but they also had low neurotensin values, as our analysis expected for this group. None of the colorectal cancer group patients displayed a combination of high neurotensin and low IL-8 values (which would be in contrast with our analysis).

Finally, one healthy control had a low neurotensin value as well as a low IL-8 value.

This pilot study[18] implicated that a blood neurotensin/IL-8 system may be used as a screening tool for colorectal cancer.

The addition of NTSR1 was of paramount importance. Neurotensin and its receptors stimulate cancer cell growth[6], mainly through binding to NTSR1, which is overexpressed in many cancer cell lines.[20]

According to our model individuals with low Neurotensin values (according to the defined cutoff) should be suspected for bearing colorectal cancer needing further assessment with colonoscopy. In this patient population having low

Neurotensin plasma values there is no need to search for IL-8 values. As a second step, individuals with high Neurotensin values and high IL-8 values should also undergo colonoscopy. Accordingly, IL-8 values should be considered as complementary to Neurotensin measurement and not as a standalone screening marker.

The diagnostic performance of a blood neurotensin/IL-8 system for colorectal cancer proved to be satisfactory. The American Cancer Society, for instance, conducted a systematic review of the literature assessing PSA performance. [21] A pooled analysis showed the estimated sensitivity of a PSA cutoff of 4.0 ng/mL as 21% in detecting prostate cancer and 51% in detecting high-grade cancers (Gleason score \geq 8) while the corresponding sensitivity using a cutoff of 3.0 g/mL was higher: 32% and 68%, respectively.

We consider the fact that not a single colorectal cancer patient in our study displayed a combination of high neurotensin and low IL-8 plasma values to be the most important finding.

Martin et al [22] conducted a thorough analysis to explore the functional significance of SORT1/NTSR1 heterodimers in HT29 cells. SORT1 shifted the neurotensin dose-response curve to the right whilst increasing maximal stimulation for ERK phosphorylation two-fold. The authors proposed that interaction between NTS1 and SORT1 produced a new means of cell activation that could prove essential for the growth effect of neurotensin. Whether this mechanism can justify the high neurotensin values (above the cut-off value) in three of our colorectal cancer group patients is uncertain. Low IL-8 values of two colorectal cancer patients were possibly due to the use of statins. The mechanism of anti-inflammatory activity of statins became

clear after finding that simvastatin or fluvastatin blocks the synthesis of IL-6 and IL-8 in isolated blood monocytes that had been stimulated by C-reactive protein or lipopolysaccharide.[23, 24] Sakoda et al. [25] showed that the dosedependent effect of simvastatin diminished IL-1a-induced IL-6 and IL-8 production in human epithelial cells.

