3.1 CONTROL(S) / COMPARATOR(S)

All individuals fulfilling the inclusion criteria will be enrolled. After the refinement of participants by the exclusion criteria blood sample will be drawn for Neurotensin and IL-8. Following the report of colonoscopy and the histology individuals will be assigned in three groups: a) group A - cancer patients, b) group B – adenoma (polyp) patients and c) group C – No pathology/normal colonoscopy. Two primary analyses will be conducted to define the cut-off plasma values for Neurotensin and IL-8 for a) diagnosing cancer (group A versus group C) and b) diagnosing adenomas (group B versus group C). A secondary analysis will be conducted comparing the performance of the Neurotensin/IL-8 system towards the 2-weeks referral and FOB test positive patients for the diagnosis of colorectal cancer and adenomas.

The reason for using participants without bowel pathology is because we need to define the "normal range" of Neurotensin and IL-8 serum values.

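### The two-step neurotensin/IL-8 rule amounts to 'either marker positive': it gains sensitivity at a cost in specificity that the protocol does not report, and the primary analysis is set marker by marker

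*Protocol*

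**What the plan says.** Section 2.1.1 reports the pilot markers one at a time. For neurotensin: "The value of plasma neurotensin ≤54.47 pg/ml at enrollment selected by ROC curves demonstrated a sensitivity of 77%, specificity of 90" per cent. For IL-8: "the value of plasma IL-8 ≥8.83 pg/ml had a sensitivity of 85%, specificity 80" per cent. It then ranks them: "Our results depicted that IL-8 should be used complementary to neurotensin due to its lower specificity".

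The same section describes the screening rule. People with low neurotensin go on to colonoscopy without IL-8 being needed. As a second step, "individuals with high Neurotensin values and high IL-8 values should also undergo colonoscopy". IL-8 is called complementary and not a stand-alone marker. The system's performance is called satisfactory. The finding given most weight is that no cancer patient had high neurotensin with low IL-8. Among the controls, "one healthy control had a low neurotensin value as well as a low IL-8 value".

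For the new study, section 3.1 states: "Two primary analyses will be conducted to define the cut-off plasma values for Neurotensin and IL-8", once for cancer against normal colonoscopy and once for adenoma against normal colonoscopy. Section 3.3 makes the ROC-selected cut-offs and the AUC the primary endpoints. Section 4.1 describes ROC curves for the classifiers of the two markers. The combined system appears as such only in the secondary comparison with two-week referral and FOB testing (sections 3.1 and 4.2).

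**The concern.** A marker with weak specificity can be contained by requiring a second positive result before acting. The two-step rule does the opposite. A positive neurotensin result is acted on alone, and IL-8 is used to add further positives among those whom neurotensin cleared. Placing IL-8 second therefore leaves all its false positives in and adds those of neurotensin.

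This matters because section 1.8 motivates the work partly by unnecessary colonoscopies, and section 1.8 THE NEED FOR A TRIAL goes on to propose changed indications for colonoscopy. The specificity of the rule as used is then a central figure, yet only single-marker specificities are printed. The title is about combined use. Followed as written, though, the primary analysis yields two cut-offs and two AUCs per comparison, and no accuracy for the rule that joins them.

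**Working it through.** **1. The plan's own figures.** The pilot had 13 cancer cases: "3 out of 13 patients in the colorectal cancer group had neurotensin values above the cut-off value defined by the ROC curve", and two others had low IL-8.
- Neurotensin sensitivity: 10/13 = 76.9%, printed as 77%. Reproduced.
- IL-8 sensitivity: 11/13 = 84.6%, printed as 85%. Reproduced.
- Controls: "Fifty-six patients and 15 healthy controls were assigned to seven groups". IL-8 specificity 12/15 = 80%. Reproduced.
- Neurotensin specificity 90%: not attainable with 15 controls (13/15 = 86.7%, 14/15 = 93.3%). With at most 15 controls, 90% and 80% occur together only at n = 10 (9/10 and 8/10). Taking all non-cancer participants instead (56 + 15 − 13 = 58) does not help: 52/58 = 89.7% fits, but 46/58 = 79.3% and 47/58 = 81.0% both miss 80%.

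**2. The logic of the rule.** Let N = neurotensin low and I = IL-8 high. Positive = N, or (not N and I). This equals N or I.

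**3. Sensitivity.** The three cases missed by neurotensin had high IL-8, and the two missed by IL-8 had low neurotensin. The rule finds 13/13 = 100% (exact 95% CI 75–100%).

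**4. Bounds on specificity from the printed rates, on common controls.**
- Upper bound: min(0.90, 0.80) = 0.80.
- Lower bound: 0.90 + 0.80 − 1 = 0.70.
- If the markers were independent in controls: 0.90 × 0.80 = 0.72.

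The control who was low on both markers is correct by IL-8 and a false positive by the rule. The rule is therefore strictly below IL-8's own specificity in the pilot.

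**5. Pilot counts.** False positives of the rule = neurotensin false positives + IL-8 false positives − overlap. At least one neurotensin false positive was IL-8 negative, so the overlap is at most the number of neurotensin false positives minus one.

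| Reading of the controls | Neurotensin FP | IL-8 FP | Overlap | Rule specificity | Exact 95% CI |
|---|---|---|---|---|---|
| n = 15, neurotensin 14/15 | 1 | 3 | 0 | 11/15 = 73.3% | 45–92% |
| n = 15, neurotensin 13/15 | 2 | 3 | 1 | 11/15 = 73.3% | 45–92% |
| n = 15, neurotensin 13/15 | 2 | 3 | 0 | 10/15 = 66.7% | 38–88% |
| n = 10, neurotensin 9/10 | 1 | 2 | 0 | 7/10 = 70.0% | 35–93% |

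The 66.7% falls under the 70% bound in step 4 only because 13/15 is below the printed 90%.

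**The case against.** The best defence is that the protocol never says that second-step use protects specificity. Calling IL-8 complementary because it is less specific can be read simply as ranking neurotensin first, and the support offered for the combination is about sensitivity. That stands. A reader might infer an explicit claim that the sequence deals with IL-8's false positives; the text does not make it. What remains is that the reason given does not support the rule described, and that the rule's specificity is missing.

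The defence can also say that the pilot counts are not established. That stands too: section 2.1.1 does not give the denominator behind the two specificities, so 67–73% depends on the reading chosen and every interval is wide. The 80% ceiling does not depend on it, provided both rates refer to the same controls.

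Thirdly, how cut-offs are chosen and joined is ordinary SAP content, and sections 3.1 and 4.2 do assess the combined system. This stands in part. The protocol names no cut-off criterion, and that is not a fault here. But the primary endpoint is fixed in the protocol, it is worded by marker, and the system enters only as a secondary comparison with another pathway.

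Finally, the consequence for participants is small: section 3 says that results do not affect their care, and the pilot cut-offs will be re-estimated. That is right, and the AUC-based sample size in section 3.5 is also unaffected.

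**Conclusion.** The point holds as a fault of rationale and of reporting that reaches the primary analysis. The rule is 'either marker positive'. In the pilot it moves sensitivity from 10/13 to 13/13. On the printed rates its specificity is between 70% and 80%, and below that of IL-8 itself. The ceiling follows from logic, given common controls; the figure of about 67–73% rests on assumed counts. All pilot figures come from cut-offs selected on the same data.

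Two stronger readings are not supported:
- A reader might project the new study's specificity from a model. Equal-variance binormal markers with AUC 0.85 and 0.81, independent within groups and cut separately at the Youden point, give 56%; a within-group correlation of 0.4 gives 61%. The protocol states neither that criterion nor independence, so such figures are illustrative at most.
- A reader might apply the specificity to the 4% cancer pick-up in section 1.8 and count every other positive as a wasted colonoscopy. That group includes people with adenomas, who are a co-primary target, and section 3.5 assumes 20–30% prevalence of adenoma or cancer.

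**What to change.** In section 2.1.1, state that the rule is 'either marker positive' and that it gains sensitivity at a cost in specificity. Print its pilot sensitivity and specificity with counts and exact confidence intervals, and give the denominator behind the 90% and 80%. Drop lower specificity as the reason for using IL-8 in this way.

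In sections 3.1, 3.3 and 4.1, for cancer against normal and for adenoma against normal, add:
- sensitivity and specificity, with confidence intervals, of the combined rule at the chosen cut-offs;
- the ROC curve and AUC of a two-marker logistic score, corrected for optimism;
- a comparison of each with neurotensin alone at the same specificity.

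Judge the pair of cut-offs on the combined rule in all participants. Deriving the IL-8 cut-off only among those above the neurotensin cut-off would be unstable: assuming 4% of 500 = 20 cancers and 77% neurotensin sensitivity, 20 × 0.23 = 4.6, or about 5 cancers, would remain.

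Both markers are planned for every participant (section 3.1), so no new data are needed. The cost is a little more analysis and a less favourable stated performance.
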